#### **6.15.4. Vital Signs and Other Physical Findings**

For the treatment-emergent categorical analyses (shift and treatment emergent), the analysis period is defined as the treatment period plus up to 30 days off-drug follow-up time. The analysis period for the continuous analyses (e.g., change from baseline by time point) is defined as the treatment period excluding off-drug follow-up time.

Vital signs and physical characteristics include systolic blood pressure (SBP), diastolic blood pressure (DBP), pulse, weight, and BMI. Original-scale data will be analyzed. When these parameters are analyzed as continuous numerical variables, unplanned measurements will be

excluded. When these parameters are analyzed as categorical outcomes and/or treatment-emergent abnormalities, planned and unplanned measurements will be included.

The planned analyses described for the laboratory analytes in Section 6.15.3 will be used to analyze the vital signs and physical characteristics.

Table JAIY.6.8 defines the low and high baseline values as well as the criteria used to define treatment-emergence based on post-baseline values. The blood pressure and pulse rate criteria are consistent with the document *Selected Reference Limits for Pulse/Heart Rate, Arterial Blood Pressure (Including Orthostasis), and Electrocardiogram Numerical Parameters for Use in Analyses of Phase 2-4 Clinical Trials Version 1.3* approved on April 29, 2015 as recommended by the Lilly Cardiovascular Safety Advisory Committee (CVSAC).

**Table JAIY.6.8. Categorical Criteria for Abnormal Treatment-Emergent Blood Pressure and Pulse Measurement, and Categorical Criteria for Weight Changes for Adults**

Parameter (Units of Measure)	Low	High
Systolic Blood Pressure (mm Hg)	≤90 (low limit) and decrease from lowest value during baseline ≥20 if >90 at each baseline visit	≥140 (high limit) and increase from highest value during baseline ≥20 if <140 at each baseline visit
Diastolic Blood Pressure (mm Hg)	≤50 (low limit) and decrease from lowest value during baseline ≥10 if >50 at each baseline visit	≥90 (high limit) and increase from highest value during baseline ≥10 if <90 at each baseline visit
Pulse (beats per minute)	<50 (low limit) and decrease from lowest value during baseline ≥15 if ≥50 at each baseline visit	>100 (high limit) and increase from highest value during baseline ≥15 if ≤100 at each baseline visit
Weight (kilograms)	(Loss) decrease ≥7% from lowest value during baseline	(Gain) increase ≥7% from highest value during baseline

**6.15.5. Special Safety Topics, including Adverse Events of Special Interest**

In addition to general safety parameters, safety information on specific topics of special interest will also be presented. Additional special safety topics may be added as warranted. The topics outlined in this section include the protocol-specified AESI.

In general, for topics regarding safety in special groups and circumstances, patient profiles and/or patient listings, where applicable, will be provided when needed to allow medical review of the time course of cases/events, related parameters, patient demographics, study drug treatment and meaningful concomitant medication use. In addition to the safety topics for which provision or review of patient data is specified, these will be provided when summary data are insufficient to permit adequate understanding of the safety topic.

### 6.15.5.1. Abnormal Hepatic Tests

Analyses for abnormal hepatic tests will involve 4 laboratory analytes: ALT, AST, total bilirubin, and ALP. In addition to the analyses described in Section 6.15.3, this section describes specific analyses for this topic.

First, the number and percentage of patients with the following abnormal elevations in hepatic laboratory tests at any time will be summarized between treatment groups:

- The percentages of patients with an ALT measurement  $\geq 3\times$ ,  $5\times$ , and  $10\times$  the central laboratory upper limit of normal (ULN) during the treatment period will be summarized for all patients with a postbaseline value and for subsets based on various levels of baseline.
  - The analysis of  $3\times$  ULN will contain 4 subsets: patients whose non-missing maximum baseline value is  $\leq 1\times$  ULN, patients whose maximum baseline is  $>1\times$  ULN but  $<3\times$  ULN, patients whose maximum baseline value is  $\geq 3\times$  ULN, and patients whose baseline values are missing.
  - The analysis of  $5\times$  ULN will contain 5 subsets: patients whose non-missing maximum baseline value is  $\leq 1\times$  ULN, patients whose maximum baseline is  $>1\times$  ULN but  $<3\times$  ULN, patients whose maximum baseline is  $\geq 3\times$  ULN but  $<5\times$  ULN, patients whose maximum baseline value is  $\geq 5\times$  ULN, and patients whose baseline values are missing.
  - The analysis of  $10\times$  ULN will contain 6 subsets: patients whose non-missing maximum baseline value is  $\leq 1\times$  ULN, patients whose maximum baseline is  $>1\times$  ULN but  $<3\times$  ULN, patients whose maximum baseline is  $\geq 3\times$  ULN but  $<5\times$  ULN, patients whose maximum baseline is  $\geq 5\times$  ULN but  $<10\times$  ULN, patients whose maximum baseline value is  $\geq 10\times$  ULN, and patients whose baseline values are missing.
- The percentages of patients with an AST measurement  $\geq 3\times$ ,  $5\times$ , and  $10\times$  the central laboratory ULN during the treatment period will be summarized for all patients with a postbaseline value and for subsets based on various levels of baseline. Analyses will be constructed as described above for ALT.
- The percentages of patients with a total bilirubin measurement  $\geq 2\times$  the central laboratory ULN during the treatment period will be summarized for all patients with a postbaseline value and subset into 4 subsets: patients whose non-missing maximum baseline value is  $\leq 1\times$  ULN, patients whose maximum baseline is  $>1\times$  ULN but  $<2\times$  ULN, patients whose maximum baseline value is  $\geq 2\times$  ULN, and patients whose baseline values are missing.
- The percentages of patients with an ALP measurement  $\geq 1.5\times$  the central laboratory ULN during the treatment period will be summarized for all patients with a postbaseline value and subset into 4 subsets: patients whose non-missing maximum baseline value is  $\leq 1\times$  ULN, patients whose maximum baseline is  $>1\times$  ULN but  $<1.5\times$  ULN, patients whose maximum baseline value is  $\geq 1.5\times$  ULN, and patients whose baseline values are missing.

Information collected from additional hepatic safety data collection forms will be provided in patient profiles.

Second, to further evaluate potential hepatotoxicity, an Evaluation of Drug-Induced Serious Hepatotoxicity (eDISH) plot using maximum postbaseline ALT divided by ULN vs. maximum postbaseline total bilirubin divided by ULN will be created that includes all patients from the safety populations for the studies included in the submission (any phase, any medication). Each subject with at least 1 postbaseline ALT and total bilirubin contributes 1 point to the plot. The measurements do not need to be taken at the same blood draw. Symbols may be used to indicate randomized treatment.

When criteria are met for hepatic evaluation and completion of the hepatic safety CRF, investigators are required to answer a list of questions (see Compound level safety standards). A listing of the collected information will be generated together with a graphical patient profile. This includes demographics, disposition, and a display of study drug exposure, AEs, medications, and the liver-related measurements over time will be provided for these patients and any additional patients meeting ALT or AST measurement greater than or equal to  $5 \times$  ULN (on a single measurement) or ALP measurement greater than or equal to  $2 \times$  ULN (on a single measurement).

#### **6.15.5.2. Hematologic Changes**

Hematologic changes will be defined based on clinical laboratory assessments. Common Terminology Criteria for Adverse Events (CTCAEs) will be applied for selected laboratory tests and are described in the compound level safety standards. These CTCAE grading schemes are consistent with both Version 3.0 and Version 4.03 of the CTCAE guidelines (CTCAE 2003, 2010).

Treatment-emergent laboratory abnormalities occurring at any time during the treatment period and shift tables of baseline to maximum grade during the treatment period will be tabulated. Planned and unplanned measurements will be included. Treatment-emergence will be characterized using the following 5 criteria (as appropriate to the grading scheme):

- any increase in postbaseline CTCAE grade from worst baseline grade
- increase to Grade 1 or above at worst postbaseline
- increase to Grade 2 or above at worst postbaseline
- increase to Grade 3 or above at worst postbaseline
- increase to Grade 4 at worst postbaseline.

Shift tables will show the number and percentage of patients based on baseline to maximum during the treatment period, with baseline depicted by the most extreme grade during the baseline period. With each shift table, a shift table summary displaying the number and percentage of patients with maximum postbaseline results will be presented by treatment group for each treatment period within the following categories:

- decreased: postbaseline category < baseline category
- increased: postbaseline category > baseline category

- same: postbaseline category = baseline category

A laboratory-based treatment-emergent outcome related to increased platelet count will be summarized in similar fashion. Treatment-emergent thrombocytosis as a laboratory-based abnormality will be defined as an increase in platelet count from a maximum baseline value  $\leq 600$  billion/L to any postbaseline value  $> 600$  billion/L (Lengfelder et al. 1998). Planned and unplanned measurements will be included.

A listing of patients with treatment-emergent thrombocytosis may be provided for safety review.

### 6.15.5.3. Lipids Effects

Lipid effects will be assessed through analysis of elevated total cholesterol, elevated LDL cholesterol, decreased HDL cholesterol, and elevated triglycerides as described in Section 6.15.3 and with TEAEs potentially related to hyperlipidemia.

Categorical analyses will be performed using National Cholesterol Education Program (NCEP) Adult Treatment Panel (ATP) III guidelines (2002) as shown in the compound level safety standards. The grade-like categories shown in this table are ordered from traditionally most desirable to least desirable for the purposes of these analyses.

Shift tables will show the number and percentage of patients based on baseline to the least desirable category during the treatment period, with baseline depicted by the least desirable category during the baseline period. With each shift table, a shift table summary displaying the number and percentage of patients with the least desirable postbaseline results will be presented by treatment group for each treatment period within the following categories:

- decreased: postbaseline category more desirable than baseline category,
- increased: postbaseline category less desirable than baseline category,
- same: postbaseline category = baseline category.

Treatment-emergent laboratory abnormalities related to elevated total cholesterol, elevated triglycerides, elevated LDL cholesterol, and decreased and increased HDL cholesterol occurring at any time during the treatment period will be tabulated using the NCEP categories shown in the compound level safety standards.

Treatment-emergent elevated total cholesterol will be characterized as follows:

- increase to categories 'Borderline high' or 'High'
- increase to category 'High.'

Treatment-emergent elevated triglycerides will be characterized as

- increase to categories 'Borderline high,' 'High,' or 'Very high'
- increase to categories 'High' or 'Very high'
- increase to category 'Very high.'

Treatment-emergent elevated LDL cholesterol will be characterized as

- increase to categories 'Borderline high,' 'High,' or 'Very high'

- increase to categories ‘High’ or ‘Very high’
- increase to ‘Very high’

Treatment-emergent abnormal HDL cholesterol will be characterized as

- decreased HDL
  - decrease to categories ‘Normal’ or ‘Low’
  - decrease to category ‘Low’
- increased HDL
  - increase to categories ‘Normal’ or ‘High’
  - increase to category ‘High’

The percentages of patients with treatment-emergent potential hyperlipidemia will be summarize by treatment, ordered by decreasing frequency in the baricitinib 4-mg group using a predefined MedDRA list of PTs that is a subset of the narrow scope PTs in the MedDRA SMQ ‘Dyslipidemia’ (code 200000026) [see Compound level safety standards].

#### **6.15.5.4. Renal Function Effects**

Effects on renal function will be assessed through analysis of elevated creatinine.

CTCAEs will be applied for laboratory tests related to renal effects as shown in the compound level safety standards. This CTCAE grading scheme is consistent with both Version 3.0 and Version 4.03 of the CTCAE guidelines. Shift tables will show the number and percentage of patients based on baseline to maximum during the treatment period, with baseline depicted by highest grade during the baseline period. Treatment-emergent laboratory abnormalities related to elevated creatinine occurring at any time during the analysis period will be tabulated. Refer to the Compound level safety standards for details.

#### **6.15.5.5. Elevations in Creatine Phosphokinase (CPK)**

Elevations in creatine phosphokinase (CPK) will be addressed using CTCAE criteria as described in the compound level safety standards. This CTCAE grading scheme is consistent with both Version 3.0 and Version 4.03 of the CTCAE guidelines. Analyses will be the same as the CTCAE analyses specified for laboratory tests related to renal function events in Section [6.15.5.2](#).

A listing of elevated CPK (CTCAE grade of 3 or above) will be provided for medical safety review.

Treatment-emergent adverse events potentially related to muscle symptoms may be analyzed, based on reported AEs. The Muscle Symptoms special search category is a pre-defined MedDRA search criteria list that contains the narrow scope terms from the Rhabdomyolysis / myopathy SMQ (code 20000002) plus selected terms from the Musculoskeletal SOC. These terms are shown in the compound level safety standards.

#### **6.15.5.6. Infections**

Infections will be defined using all the PTs from the Infections and Infestations SOC as defined in MedDRA. Serious infection will be defined as all the infections that meet the SAE criteria.

The number and percentage of patients with TEAEs of infections, serious infections, and infections resulting in permanent study drug discontinuation will be summarized by treatment group using MedDRA PTs. The proportion of patients developing skin infections requiring antibiotic treatment by Week 16 will also be summarized on the overview of infections table.

The number and percentage of patients with TEAEs of infections by maximum severity will be summarized by treatment group using MedDRA PTs.

Treatment-emergent infections will be reviewed in context of other clinical and laboratory parameters via a listing (details see Compound level safety standards).

The TEAE infections will be further analyzed in terms of potential opportunistic infection, herpes zoster and herpes simplex. Summary of HBV DNA monitoring results and association between infection and neutropenia/lymphopenia will also be provided in the context of infections.

### **Opportunistic infection**

To identify potential opportunistic infections (POIs), the following approach will be used:

- identifying the POIs using a list of MedDRA PTs (refer to the compound level safety standards).

Potential opportunistic infections identified through these search approaches may be combined in one list for medical assessment and final classification of whether the case met the modified Winthrop definitions for opportunistic infections (OIs).

A final listing for OIs will be provided for the CSR and to assist the composition of patient narratives.

### **Herpes zoster**

Cases of herpes zoster will be further classified as follows:

- localized or non-multidermatomal-involvement of the primary and/or adjacent dermatomes only
  - complicated – documented ocular (cornea or deeper structure; for example, iritis, keratitis, retinitis, etc.) or motor nerve involvement (e.g., palsy; post herpetic neuralgia [PHN] does not meet criteria for motor nerve involvement).
  - uncomplicated-localized or non-multidermatomal cases that are not complicated
- multidermatomal-involvement beyond primary and adjacent dermatomes (that is, >3 contiguous dermatomes) or involvement of two or more non-contiguous dermatomes
  - complicated-documented ocular (cornea or deeper structure; for example iritis, keratitis, retinitis, etc.) or motor nerve involvement
  - uncomplicated-multidermatomal cases
- disseminated-systemic infection, visceral or widespread cutaneous (e.g.,  $\geq 5$  dermatomes or 3 to 4 dermatomes including at least 1 non-contiguous).

- Recurrent - >1 infection occurring in an individual patient during the course of participation in the baricitinib clinical program.

All herpes zoster will undergo medical review to determine the classification as described above.

A summary of herpes zoster table will be provided. The summary table will also include event maximum severity, seriousness, whether resulting in temporary study drug interruption, whether resulting in study drug discontinuation, whether treated with antiviral medication, and event outcome. The incidence rate adjusted for observation time will also be provided (as defined in Section 6.15.2). Of note, in the context of herpes zoster, antiviral medication treatment is defined as that the medication was initiated at the event start date, or within 30 days before or after the event start date. The antiviral medication for herpes zoster includes but not limited to Aciclovir, Brivudine, Cidofovir, Famciclovir, Foscarnet, Ganciclovir, Penciclovir, Valaciclovir, Valganciclovir, Vidarabine (best presented by J05AB, J05AC, J05AE, and J05AH Anatomical Therapeutic Classification codes). Medical representatives will review the concomitant medication list prior to database lock and make adjustment of the above list if necessary.

If a patient has more than 1 event of herpes zoster, the event with the maximum severity will be used in these summary tables. If more than 1 event of herpes zoster occurs with the same severity, the event with the longest duration will be used in the summary table.

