6.2. Exclusion Criteria

Patients will be excluded from study enrollment if they meet any of the following criteria:

Medical Conditions Related to Atopic Dermatitis

- [11] are currently experiencing or have a history of other concomitant skin conditions (e.g., psoriasis or lupus erythematosus) that would interfere with evaluations of the effect of study medication on AD.
- [12] have had an important side effect to TCS (e.g., intolerance to treatment, hypersensitivity reactions, significant skin atrophy, and systemic effects), as assessed by the investigator or treating physician that would prevent further use.
- [13] patients who, in the opinion of the investigator, are currently experiencing or have a history of erythrodermic, refractory, or unstable skin disease that requires frequent hospitalizations and/or intravenous treatment for skin infections that may interfere with participation in the study.
- [14] a history of eczema herpeticum within 12 months prior to screening.
- [15] a history of 2 or more episodes of eczema herpeticum in the past.
- [16] patients who are currently experiencing a skin infection that requires treatment, or is currently being treated, with topical or systemic antibiotics.

Note: Patients may not be rescreened until at least 4 weeks after the date of their previous screen failure and at least 2 weeks after resolution of the infection.

- [17] have any serious concomitant illness that is anticipated to require the use of systemic corticosteroids or otherwise interfere with study participation or require active frequent monitoring (e.g., unstable chronic asthma).
- [18] have been treated with the following therapies:
 - a. monoclonal antibody (e.g., ustekinumab, omalizumab, and dupilumab) or fusion proteins that target inflammatory pathways (e.g., etanercept) for less than 5 half-lives prior to randomization.
 - b. received prior treatment with any oral JAK inhibitor (e.g., tofacitinib and ruxolitinib) <4 weeks prior to randomization
 - c. received any parenteral corticosteroid administered by intramuscular or intravenous injection within 6 weeks prior to planned randomization (Visit 2) or are anticipated to require parenteral injection of corticosteroids during the study.
 - d. have had an intra-articular corticosteroid injection within 6 weeks prior to planned randomization (Visit 2).

Note: Intranasal or inhaled steroid use is allowed during the trial.

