### **Herpes simplex**

A summary analysis of herpes simplex will be provided. Herpes simplex will be defined based on MedDRA PT as listed in the compound level safety standards (both narrow and broad terms in the herpes simplex section). The list needs to be reviewed by medical prior to data locks (final and interim). The summary table will include event maximum severity, seriousness, whether resulting in temporary study drug interruption, whether resulting in study drug discontinuation, and whether treated with antiviral medication.

If a patient has more than 1 event of herpes simplex, the event with the maximum severity will be used in these summary tables. If more than 1 event of herpes simplex occurs with the same severity, the event with the longest duration will be used in the summary table.

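### The SAP's start-date rule would tabulate an antiviral course that ended before herpes zoster onset as treatment of the zoster

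*SAP*

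**What the plan says.** SAP 6.15.5.6 (Infections), under Herpes zoster, plans a summary table whose items include "whether treated with antiviral medication, and event outcome". The antiviral item has its own definition: "in the context of herpes zoster, antiviral medication treatment is defined as that the medication was initiated" inside a set window, and the qualifying start is "initiated at the event start date, or within 30 days before or after the event start date". The definition does not use the stop date, overlap with the zoster event, or the reason for prescribing.

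Drugs qualify by name or by four ATC codes, from an open list: "The antiviral medication for herpes zoster includes but not limited to Aciclovir, Brivudine, Cidofovir, Famciclovir" and further agents.

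Two reviews are described in the same subsection. One concerns the drugs: "Medical representatives will review the concomitant medication list prior to database lock and make adjustment of the above list if necessary". The other concerns the cases: "All herpes zoster will undergo medical review to determine the classification as described above".

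**The concern.** A table item that says a zoster event was treated should mean that an antiviral was given for it, or at least during it. A rule based on start date alone does not ensure that. A short course begun four weeks before onset and stopped three weeks before onset satisfies the definition just as a course begun on the day of onset does.

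Antiviral use for other reasons is foreseeable. Protocol 7.7.1 permits systemic anti-infectives without tying them to zoster. The herpes simplex table in the same SAP section also reports "whether treated with antiviral medication", so antiviral courses for another infection are expected.

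At stake is whether the table can separate three situations: zoster treated at or after onset, zoster that was not treated but followed a recent antiviral course, and zoster that arose while an antiviral was already being taken. Infections including herpes zoster are adverse events of special interest (Protocol 9.2.2), so the table will be read closely even though nothing in it is formally tested.

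**Working it through.** The SAP states no figure for this item, so there is none to reproduce. The check is a count of days, followed by a check for any other text that closes the gap.

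**Inputs**
- Window: start date from day −30 to day +30 around event start, which is day 0 (SAP 6.15.5.6, Herpes zoster).
- Course length L: not in the documents. A range of 5 to 21 days is assumed for the arithmetic only and implies nothing about how zoster should be treated.

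**Window.** 30 days before + 1 onset day + 30 days after = 61 qualifying start days, of which 30 precede onset.

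**Finished courses.** A course of L days started on day −s (s = 1 to 30) has its last day on day −s + L − 1. It is finished before onset when −s + L − 1 < 0, that is, when s ≥ L. The number of such start days is 30 − L + 1 = 31 − L. The other L − 1 pre-onset start days give a course still running at onset.

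| Assumed L (days) | Pre-onset start days with the course finished before onset (31 − L) | Pre-onset start days with the course still running at onset (L − 1) | Last day of a course started on day −30 |
|---|---|---|---|
| 5 | 26 | 4 | −26 |
| 7 | 24 | 6 | −24 |
| 10 | 21 | 9 | −21 |
| 14 | 17 | 13 | −17 |
| 21 | 10 | 20 | −10 |

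All 30 pre-onset start days count as zoster treatment under the present rule. If the stop date had to fall on or after event start, only the third column would count. A tolerance of t days would lower the excluded number to 31 − L − t.

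**Is the gap closed elsewhere?**
- The medication review described in the zoster subsection adjusts which drugs are on the list. It is not said to look at the dates or purpose of individual courses.
- The case review settles the zoster classification: dermatomal extent, complications, dissemination, recurrence. It is not said to decide whether a case was treated.
- SAP 6.15.5 provides patient profiles or listings when needed, covering concomitant medication, and SAP 6.15.5.6 provides a listing for treatment-emergent infections. These let a reader see the timing, but neither changes how the table item is derived.
- SAP 6.11 defines concomitant therapy by start and end, so the plan already relies on medication end dates.

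**The case against.** The strongest reply is that a wrong entry needs three things in one patient: zoster on study, a listed antiviral started in the preceding 30 days and finished before onset, and no other qualifying antiviral. If the patient also received one for the zoster, the entry is right. The trial has about 300 patients and 16 weeks of treatment, and the documents give no rate for any of these events. A look-back also has a reasonable purpose, since onset dates are imprecise and an antiviral may be started before the recorded onset. The listings allow individual cases to be checked, and the compound level safety standards cited for the infection listing are not available here.

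Most of this stands, and it limits the weight of the point. It does not rescue the definition: a course that ended well before onset is not explained by date error, and a listing does not correct a table derived by rule.

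Some stronger readings are not supported.
- A reader might infer that the eligibility rules make unrelated antiviral use likely, because only "a history of 2 or more episodes of eczema herpeticum in the past" excludes a patient on number of episodes. But Protocol 6.2 also excludes eczema herpeticum in the 12 months before screening (criterion 14) and symptomatic herpes simplex at randomization (criterion 27c). One older episode says nothing about antiviral use in the month before an on-study zoster event.
- A reader might infer a large distortion. With 1 to 4 zoster events in an arm, one wrong entry moves the treated share by 1/4 to 1/1, or 25 to 100 percentage points. That event count is assumed, and the same arithmetic fits any yes/no item in a table of rare events.
- A reader might infer that the account of how zoster resolved is compromised. Event outcome is a separate item and does not use the window, and no planned analysis examines zoster arising during antiviral therapy.

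**Conclusion.** The point holds as a small defect of definition. If the SAP is followed as written, an antiviral course completed before zoster onset is tabulated as treatment of that zoster. The text establishes that this can happen; it does not establish that it will. The day counts rest on the assumed course length, but the direction does not: any course shorter than 31 days has at least one pre-onset start day for which it is over before onset and still counts.

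One descriptive item is affected. Severity, seriousness, study drug interruption and discontinuation are recorded independently of the antiviral window, as are incidence, classification and outcome. No efficacy result is touched. The improvement is worth making because it is cheap, not because a conclusion of the trial depends on it.

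**What to change.** Amend the definition in SAP 6.15.5.6, Herpes zoster:

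- Keep the 30-day start-date window on both sides of event start.
- For a course started before event start, also require the recorded stop date to be on or after event start, allowing a few days' tolerance for date error. Fix that number in the SAP before unblinding.
- Show a course that ended before onset as prior antiviral use, not as treatment.
- Flag a course already running at onset separately and settle it by blinded case-level review before database lock, using the recorded indication where the CRF captures one. The documents do not confirm that it does.

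The window should stay. Replacing it with an overlap test alone would bring in long-term antiviral use begun months earlier, which the present rule leaves out, and would still count an overlapping course given for another infection.

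The cost is about one sentence in the SAP, a stop-date condition in the derivation, and individual review of a few cases. The downside is that a course with a wrongly recorded stop date could be misclassified.
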